Several methodological considerations will allow for a more accurate account of the patterns of functional activation for the participants with aphasia. First, an event-related study design will be used in which brain responses to correctly and incorrectly named items can be distinguished and compared across time-points [26]. Secondly, measurements of hemodynamic response (HRF), which are used to estimate the neural response related to the naming event, will be calculated for each individual participant. This is important because individuals with aphasia are known to have delayed HRF or HRF that is decreased in amplitude, resulting in erroneous or underestimated measures of brain activity when canonical HRF estimates are used [43]. Third, dynamic (activity-dependent), directional coupling, known as effective connectivity, will be estimated for regions in the RH and LH to measure interactivity changes across time resulting from rTMS.

C.1 Procedures:

The schedule of study procedures across the 13 study sessions is summarized in Figure 4. During the initial session, enrolled participants will be assessed with the Philadelphia Naming Test (PNT; [44]) and the Comprehensive Aphasia Test (CAT; [45]). In cases where apraxia of speech is suspected, the Apraxia Battery for Adults (ABA-2; [46]) may be administered in whole or in part. Participants may also be assessed with other psycholinguistic and naming measures. The first session will conclude with the baseline MRI scan (described in detail below). If, following the screening session, a participant is found to be eligible they will be scheduled for all remaining study-related visits.

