The second visit will begin with the first rTMS session (also described below) which will then be followed directly by the post-rTMS MRI scan. Starting the following day, the subsequent nine sessions will consist only of rTMS for a total of 10 rTMS sessions. The sessions in the rTMS series will take place daily across two weeks excluding weekends. A post-testing session, scheduled the week after the final rTMS session, will include an MRI scan and repeat administration of the language assessments that were administered during the screening visit. A final follow-up session, identical in design to the post-testing session, will be scheduled in an additional 7-10 weeks. All study-related evaluations will be administered by the PI (a licensed speech-language pathologist) or in Year 2 by the staff speech-language pathologist. Study participants will receive up to \$275 for time and local travel expenses and up to an additional \$1500 to defray lodging expenses incurred as part of study participation, to be pro-rated if they do not complete all study procedures (including follow-up visits).

Participants will be pseudo-randomly assigned to an rTMS treatment group (priming stimulation vs no priming stimulation) depending on the outcome of their baseline fMRI (described in C1.1, below). That is, an equal number of participants with and without baseline RH PTr activation will be approximated in each group.

C.1.1 MRI Procedure

fMRI Overt Confrontation Picture Naming Task. Images will be acquired using a 3.0 Tesla parallel-acquisition, echo-planar equipped Siemens MRI scanner. Participants will lay supine in the scanner wearing hearing protection and over-ear headphones. Their heads will be secured with foam padding to minimize movement.

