During the fMRI session, picture stimuli will be projected onto a screen placed at the rear of the MRI scanner with E-Prime 2.0 (Psychology Software Tools) software, which subjects will be able to see via a head coil-mounted mirror. Participants will be asked to name the pictures aloud as quickly and accurately as possible. Picture stimuli will consist of black and white line drawings of objects drawn from the Center for Research in Language International Picture Naming Project Database (CRL-IPNP; [47]) and will exclude any items that overlap with the CAT and PNT to avoid repetition effects. The pictures will be presented for 2000 msec with a between-picture ISI between 4-16 seconds, jittered by 2 second intervals. Including longer ISIs will allow the HRF to intermittently return to levels approaching baseline in order to more accurately model individual HRF responses. Between pictures, participants will be asked to fixate on a black crosshair that will be centered on the screen. Naming responses will be recorded via a MR-compatible fiber-optic dual-channel noise cancelling microphone (Optoacoustics Ltd.) to allow for offline scoring of both accuracy and response latency. The fMRI scan will consist of 4 runs (experiment segments) of approximately 40 pictures each; with each run lasting approximately 5 minutes. Picture stimuli will be balanced across runs for average item difficulty [42]. The design of this task is similar to the design used by Postman-Caucheteux and colleagues [26] with participants with aphasia, suggesting that it is feasible with this population.

C 1.2 TMS Procedure

We will use a Magstim Rapid or Rapid2 Magnetic Stimulator (Woburn, MA) with the MagStim Double 70 mm alpha coil, to generate the pulses used to find the motor threshold, and the Magstim Double 70mm air cooled coil to generate the pulses of the rTMS treatment during this study. Before starting each treatment, subjects will be instructed to insert earplugs to lessen any possible adverse effect on hearing.

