C2.2 fMRI Processing/Data Analysis: All processing will be performed using SPM12 (The Wellcome Trust Centre for NeuroImaging, UCL, UK). The concatenated functional image sequences (runs) will be preprocessed with standard fMRI analysis routines that include slice time acquisition correction, realignment,

registration to structural images, spatial normalization, and spatial smoothing. The data will also be filtered for low frequency scanner drift.

Within-subject data (first level) will be analyzed using a general linear model with a finite impulse response (FIR) basis function to model the individual HRF. For each participant, we will generate an individualized map of brain activity for the contrast of naming > baseline (crosshair fixation) including factor of MRI session for both correct and incorrect responses. Movement parameters will be entered as regressors of no interest to control for participant head movement in the scanner. Activation maps for all contrasts will be thresholded to $p=0.05$ (cluster corrected using Family-Wise Error (FWE)). Resulting contrast values (effect sizes) for each contrast will be entered into a second level/random effect analysis by group (Group A: inhibitory only rTMS vs Group B: excitatory primed inhibitory rTMS). Region of Interest (ROI) analysis will be performed to estimate activation for RH PTr for all described contrasts using the MarsBaR toolbox for SPM.

To assess the relative contribution of the right versus left hemisphere (hemispheric lateralization) to the fMRI naming task, whole brain laterality indices (LI) will be calculated for each scan using the LI-toolbox for SPM [50]. As LI calculation relies on the computation $LI = (Left-Right) / (Left+Right)$, a negative value indicates a right hemispheric dominance and a positive value indicates a left hemispheric dominance. LI values will be generated using t-maps from the first level analyses described above.

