Dynamic causal modeling (DCM) will be used to estimate effective connectivity changes due to inhibitory rTMS across time. Regions to be included in the DCM analysis will be derived from clusters of contiguous voxels surviving an omnibus F-test for the effect of interest (correct naming > crosshair fixation) at $p < 0.001$ uncorrected from the first-level fMRI analysis. Regions will be constrained to only include those clusters that fall within the traditionally outlined “language network” in the LH (inferior frontal lobe, temporal lobe, and portions of the inferior and posterior parietal lobe, [51]) and the corresponding RH homologues. The effective connectivity model (estimate of coupling and weights between these regions) will be estimated via post-hoc network discovery methods [52]. This method uses Bayesian model selection methods to select the model that was the most likely to have generated the time series data from all possible combinations of bi-directional connections between the regions. Coupling weights for interhemispheric connections will be summed for each participant for each scanning session. Other post-hoc analyses of the DCM results may be undertaken to explore both inter- and intra-hemispheric network level effects of the rTMS.

Finally, change in naming accuracy on the PNT across sessions will be correlated with change in LI, functional activation in RH PTr, and interhemispheric effective connectivity across sessions. A positive correlation between naming gains and 1) a left-hemisphere directed LI shift, and 2) a decrease in RH inhibition of LH (more positive RH to LH directional coupling weights) will support Hypothesis 1a and 1b, respectively. A positive correlation between the magnitude of pre-TMS RH PTr activation and 1) decrease in RH PTr activation across scan sessions, and 2) magnitude of left-hemisphere directed LI shift will support Hypothesis 2a and 2b, respectively. A significant interaction of group and session (analysis C2.1) suggesting that Group B receiving the 6 Hz primed inhibitory rTMS showed greater naming improvement across time will support Hypothesis 3.

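### Hypothesis 2a correlates baseline RH PTr activation with the fall from that same single scan, so a positive correlation is expected even if rTMS does nothing

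*Combined protocol and SAP*

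**What the plan says.** The last paragraph of C2.2 (fMRI Processing/Data Analysis) sets the decision rule. Support for Hypothesis 2a is "A positive correlation between the magnitude of pre-TMS RH PTr activation and 1) decrease in RH PTr activation across scan sessions". For Hypothesis 3 the same paragraph asks for a significant interaction; for 2a it asks only that the correlation be positive.

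Section C.1 (Procedures) fixes the scans. One precedes stimulation: "The first session will conclude with the baseline MRI scan". Three follow. The first rTMS session is "followed directly by the post-rTMS MRI scan". Then comes "A post-testing session, scheduled the week after the final rTMS session, will include an MRI scan", and last "A final follow-up session, identical in design to the post-testing session". The plan does not say which of the three defines the decrease.

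C.1.1 states: "The fMRI scan will consist of 4 runs (experiment segments) of approximately 40 pictures each". C2.2 adds: "The concatenated functional image sequences (runs) will be preprocessed". It estimates RH PTr activation by a region-of-interest analysis for every contrast. Contrast values are "entered into a second level/random effect analysis by group", but whether the 2a correlation pools the groups is not stated.

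Under C 1.2, both groups receive active 1 Hz rTMS and Group B has 6 Hz priming first. The Study timeline plans 6 participants in Year 1 and 10 in Year 2.

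**The concern.** The statistic has the form corr(baseline, baseline − later). A participant whose baseline reading is too high by chance scores high on the predictor and, because the later reading tends to fall back, also shows a large decrease. This is regression to the mean, and it pushes the correlation upward whether or not rTMS works.

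rTMS need not be inert for this to happen. If it lowered activation by the same amount in everyone, the correlation would not change, because subtracting a constant leaves it as it was. The rule therefore does not separate dependence of response on baseline, which is what 2a asks, from no dependence.

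Section A.3.1 treats pre-rTMS imaging of RH PTr as essential for interpreting the rTMS effects, and 2a is an analysis that uses it in that way. A spurious finding here could shape the follow-on work described under Future Directions.

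**Working it through.** The plan gives no power, alpha or expected correlation for 2a, so there is no figure of its own to reproduce.

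**Inputs from the documents.** One pre-rTMS scan and three later scans (C.1); n = 6 + 10 = 16 (Study timeline); no unstimulated arm (C 1.2).

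**Assumptions, not in the documents.** Two-sided 0.05; one later scan; equal variances at the two scans; stable true activation; reliability ρ of 0.4, 0.6, 0.8 or 0.9; 16/2 = 8 per group (no group size is stated). A case with 12 complete pairs is shown as an illustration only.

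**Expected correlation with no effect.** Write each scan as true score (variance ρ) plus independent error (variance 1 − ρ): X at baseline, Y later.

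- Cov(X, X − Y) = 1 − ρ
- Var(X) = 1 and Var(X − Y) = 2(1 − ρ)
- corr(X, X − Y) = (1 − ρ)/sqrt(2(1 − ρ)) = sqrt((1 − ρ)/2)

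This gives sqrt(0.30) = 0.55, sqrt(0.20) = 0.45, sqrt(0.10) = 0.32 and sqrt(0.05) = 0.22. It is zero only if the measurement is perfectly reliable.

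**How often it is significant.** The critical r is 0.497 at n = 16, 0.514 at n = 16 adjusted for group, and 0.707 at n = 8. Simulating normal data with no rTMS effect (at least 100,000 trials per setting) and counting significant positive r, where 2.5% is nominal:

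| Reliability | 0.4 | 0.6 | 0.8 | 0.9 |
|---|---|---|---|---|
| Expected r | 0.55 | 0.45 | 0.32 | 0.22 |
| 16 pooled | 63% | 43% | 22% | 13% |
| 16, adjusted for group | 60% | 40% | 21% | 12% |
| 12 pooled | 49% | 32% | 17% | 10% |
| One group of 8 | 30% | 20% | 11% | 7% |

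A Fisher z approximation for the ends of the range gives 60% to 13% at n = 16 and 28% to 7% at n = 8.

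**Other readings of the rule**, reliability 0.4 to 0.9:

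- Decrease to the mean of the three later scans: 86% to 18% (n = 16), 49% to 9% (n = 8).
- Linear slope over the four scans: 57% to 12% and 27% to 7%.
- Any positive r counts, as the wording literally allows: 99% to 81% and 94% to 72%.

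**Why the two alternatives remove the artefact.** If the predictor comes from two baseline runs and the baseline value in the change score from the other two, no run-level error is shared and the no-effect covariance is zero. In Oldham's method, Cov(X − Y, (X + Y)/2) = (Var X − Var Y)/2, which is zero when the variances are equal. In simulation at n = 16, each gives significant positive r in about 2.5% of no-effect trials when its condition holds.

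**The case against.** The mechanism and the arithmetic are hard to dispute. The serious objections are about how far the numbers describe this trial and how good the remedy is.

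- **The percentages rest on assumptions.** Alpha, reliability, the change score and the group size are all absent from the plan, and part of the text between sections B and C.1, which may hold the wording and priority of the hypotheses, was not available. This stands for the size of the effect. It does not touch the direction: C2.2 itself states the decision rule, and no visible text corrects for the shared scan.
- **Each alternative fails under a plausible condition.** This also stands. Oldham's equal-variance condition may be strained by the trial's own aim: if naming improves, later scans contain more correct trials, and error in a correct-naming contrast may fall. A 25% fall in later error variance gives false support of 5.1/4.3/3.7% at reliability 0.4/0.6/0.8. Split runs do not remove error common to the whole baseline session; if all error were of that kind they would do no better than the raw correlation.
- **The contrast is not named.** C2.2 models correct and incorrect responses and runs the region-of-interest analysis for all contrasts, so a test fixed in every other respect could still be run on either. This stands, and the fix below includes it.
- **The alternatives have little power.** True, but this is no reason to keep the raw test. At reliability 0.4 and n = 16 the raw test is significant in 82% of trials with a true 30% proportional reduction and in 63% with none, so most of its apparent power is artefact.

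**Conclusion.** The concern holds. Followed exactly, the rule for 2a yields a positive correlation as the expected result under no rTMS effect, and equally under an effect that is the same for everyone. That conclusion needs only imperfect reliability, roughly equal scan variances and a single baseline scan. Even at a reliability of 0.9 the pooled false-support rate is about five times nominal (13% against 2.5%). The full range, 63% to 13% pooled and 30% to 7% in a group of 8, depends on the assumptions listed above and is not a measured property of this trial.

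The scope is limited. Hypothesis 3 and the group comparison of naming use the separate model in C2.1 and are untouched. For 2b, baseline RH PTr activation and baseline LI may share error from the same scan, to an unknown extent. The point should be corrected before analysis, but it does not undermine the trial as a whole.

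**What to change.** Add to C2.2:

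> The raw correlation of baseline RH PTr activation with its decrease is expected to be positive with no effect and will not by itself count as support for Hypothesis 2a.

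Then name in advance one later scan, the activation contrast, the alpha and whether the groups are pooled. Fix one of the two tests below before analysis and report its estimate with a 95% confidence interval.

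1. **Split runs.** Take the predictor from two of the four baseline runs and the baseline value in the change score from the other two. Because the plan concatenates runs, separate first-level RH PTr contrasts are needed for each half. Each half has about 2 × 40 = 80 pictures, fewer if the contrast uses only correct or only incorrect responses.
2. **Oldham's method.** Correlate baseline minus the named later scan with the mean of those two values.

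The choice turns on which is thought the lesser risk: session-wide baseline error (harms split runs) or unequal error variance and response that varies for other reasons (harm Oldham). For 2b, add a caveat on possible shared scan error and, optionally, take RH PTr activation and LI from different baseline runs.

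The cost is SAP wording and one re-coded test, with no new data. The statistical cost should be stated (n = 16 unless noted; % significant positive):

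| Reliability | 0.4 | 0.6 | 0.8 | 0.9 |
|---|---|---|---|---|
| **No effect** | | | | |
| Split, 25% of error session-level | 5.4 | 4.8 | 4.2 | 3.7 |
| Split, 50% session-level | 12.3 | 10.0 | 7.1 | 5.4 |
| Split, 75% session-level | 28.5 | 20.7 | 12.4 | 8.2 |
| Oldham, later error variance halved | 11.0 | 7.8 | 5.4 | 4.3 |
| **True 30% proportional reduction** | | | | |
| Oldham | 6.4 | 11.6 | 28.3 | 56.8 |
| Split | 4.4 | 7.1 | 16.7 | 37.4 |
| Oldham, n = 8 | 4.5 | 6.8 | 13.6 | 26.6 |
| Split, n = 8 | 3.6 | 4.8 | 8.9 | 17.4 |
| **Same, plus unrelated response variation (SD half the true-score SD)** | | | | |
| Oldham | 4.0 | 5.2 | 7.9 | 10.3 |
| Split | 4.4 | 6.7 | 13.9 | 24.3 |

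With that unrelated variation and no dependence on baseline, Oldham's positive rate drops to 1.7/1.2/0.8/0.5%, so it is then biased against 2a. Under either test, a non-significant result would not be evidence against 2a, and the plan should say so.
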